## 5.0 Study Objectives

## 5.1 Primary Objective:

To compare the real – life effectiveness of adalimumab to topical and traditional systemic agents in the management moderate to severe Plaque PS.

# 5.2 Secondary Objectives:

- i. To compare the real life effectiveness of adalimumab to topical and traditional systemic agents in the prevention of development of articular and extra-articular manifestations in patients with moderate to severe Plaque PS.
- ii. To describe the profile and regional variation in terms of demographics, disease parameters, flare up trigger, comorbidities and concomitant medication use of Canadian patients with moderate to severe Plaque PS.
- iii. To describe the current practices and regional variation among Canadian dermatologists with respect to the screening and detection of articular manifestations indicating onset of PsA in patients with moderate to severe Plaque PS.

- iv. To describe the incidence of and risk factors for the development of articular and extra-articular manifestations in Canadian patients with moderate to severe Plaque PS.
- v. To describe the current population based burden of illness incorporating Health Care Utilization, Health Care Costs, Quality of Life, Psychological impact Work Productivity of moderate to severe Plaque PS in Canada.
- vi. To assess the impact of topical agents, traditional systemic agents and adalimumab on the Plaque PS related burden of illness incorporating Health Care Utilization, Health Care Costs, Quality of Life, Psychological impactWork Productivity in Canada.
- vii. To provide an ongoing assessment of the safety and tolerability of adalimumab, systemic and topical agents used in the management of moderate to severe Plaque PS in Canada.

#### 5.3 Study Endpoints

## 5.3.1 Primary Endpoint

The primary effectiveness outcome measure for the current study will be the physician global assessment (PGA) of "0" or "1" indicating clear or minimal disease according to the following classification:

| Score   | Category | Description                                                           |
|---------|----------|-----------------------------------------------------------------------|
| 0 Clear | Clear    | Plaque elevation = 0 (no elevation over normal skin)                  |
|         |          | Scaling = 0 (no scale)                                                |
|         |          | Erythema = $\pm$ (hyper pigmentation, pigmented macules, diffuse      |
|         |          | faint pink or red coloration)                                         |
| 1       | Minimal  | Plaque elevation = $\pm$ (possible but difficult to ascertain whether |
|         |          | there is a slight elevation above normal skin)                        |
|         |          | Scaling = $\pm$ (surface dryness with some white coloration)          |
|         |          | Erythema = up to moderate (up to definite red coloration)             |

| Score   | Category | Description                                                           |
|---------|----------|-----------------------------------------------------------------------|
| 2       | Mild     | Plaque elevation = slight (slight but definite elevation, typically   |
|         |          | edges are indistinct or sloped)                                       |
|         |          | Scaling = fine (fine scale partially or mostly covering lesions)      |
|         |          | Erythema = up to moderate (up to definite red coloration)             |
|         | Moderate | Plaque elevation = moderate (moderate elevation with rough or         |
| 3 Moder |          | sloped edges)                                                         |
|         |          | Scaling = coarser (coarse scale covering most of all of the lesions)  |
|         |          | Erythema = moderate (definite red coloration)                         |
|         | Severe   | Plaque elevation = marked (marked elevation typically with hard or    |
|         |          | sharp edges)                                                          |
| 4       |          | Scaling = coarse (coarse, non tenacious scale predominates            |
|         |          | covering most or all of the lesions)                                  |
|         |          | Erythema = severe (very bright red coloration)                        |
|         |          | Plaque elevation = very marked (very marked elevation typically       |
|         |          | with hard sharp edges)                                                |
| 5       | Very     | Scaling = very coarse (coarse, thick tenacious scale over most of all |
|         | severe   | of the lesions; rough surface)                                        |
|         |          | Erythema = very severe (extreme red coloration; dusky to deep red     |
|         |          | coloration)                                                           |

The primary outcome measure will be the percent of patients with PGA score of  $\leq 1.0$  at 6 months of treatment.

# 5.3.2 Secondary Endpoints:

The following secondary endpoints will be assessed:

- i. Time to achieving  $\underline{PGA} \le 1$  over 24 months of follow up.
- ii. Percent of patients with  $\underline{PGA} \le 1$  at 3, 12, 18 and 24 months
- iii. Signs and symptoms suggesting onset of PsA:
  - i. Change in the modified Psoriasis and Arthritis Screening Questionnaire (PASQ). This is an 11 item tool that ascertains self reported presence of joint pain and swelling. This will be assessed at 3, 6, 12, 18 and 24

#### months.

- iv. Change in Body Surface Area (BSA) of psoriasis involvement at 6, 12, 18 and 24 months. The BSA is an indicator of disease severity and the affected area is expressed as a percentage of the total body surface area.
- v. Change in Patient Global Assessment of Disease Activity based on a six point Likert Scale at 3, 6, 12, 18 and 24 months.
- vi. Change in the Dermatology Quality of Life Index (DLQI) at 3, 6, 12, 18 and 24 months. The DLQI is a self administered questionnaire comprised of 10 items assessing a patient's skin and problems associated with skin disease. The 10 questions in the DLQI converge into six domains that measure symptoms and feelings, daily activities, leisure, work and / or school, personal relationships and satisfaction with treatment.
  - i. Proportion of patients achieving and time to  $\underline{DLQI} \le 1$  through the 24 months of treatment.
- vii. Change in Beck Depression Inventory at 6, 12 and 24 months: This will be used to assess the presence and severity of depression. It consists of 21 items converging to two scales measuring somatic and affective components of depression. The questions assess hopelessness and irritability, cognition such as guilt or feelings of being punished, as well as physical symptoms such as fatigue, weight loss and loss of interest in sex. Given the important emotional and social impact of psoriasis assessing psychological impairment is important in order to fully appreciate the impact of the disease and effect of treatment on the patient's life.
- viii. Change in Medical Outcomes Study Short Form 12 (SF-12) at 6, 12 and 24 months. The SF-12 Health is a 12-item general health self administered

- questionnaire consisting of 8 scales measuring Physical Function, Physical Role limitations, Vitality, General Health, Pain, Social Function, Emotional Role limitations, and Mental Health.
- ix. Change in Work Limitation Questionnaire at 6, 12 and 24 months. The WLQ is a self-administered questionnaire comprised of 25 questions. It assesses the degree to which the patient's work is affected due to health problems or health-related productivity loss. The 25 questions are further divided into four scales: time management, physical demands, mental-interpersonal demands and output demands. The scoring for the WLQ ranges from 0 (none of the time) to 100 (all of the time) and represent the portion of time in the prior two weeks that those answering the questionnaire were limited in their abilities while at work. Furthermore, an algorithm is present that can convert scores obtained using the WLQ into an estimate of productivity loss. Considering the important effect of psoriasis on the patient's ability to deal with the emotional and physical demands of employment, the assessment of the impact of disease and treatment on work related productivity loss is highly relevant.
- x. Health Care Utilization Questionnaire through the 24 months of treatment. This will be a descriptive self administered series of questions aimed at measuring the patient's health care utilization and economic impact of the disease. More specifically the questionnaire will ascertain the frequency of physician visits, utilization of other health care professionals, visits to clinics, emergency rooms and hospitalizations that are related to psoriasis. In addition, use of prescription and non–prescription medications for the management of psoriasis will be determined. Out of packet expenses for medications and health care will be assessed. The patient's occupation and household income range will be used as a proxy to socioeconomic status.
- xi. Compliance with treatment will be assessed through the 24 months of treatment

by self report of missed topical applications, medication doses or adalimumab injections.

- xii. Change in medical history and concomitant medication use through the 24 months of treatment will be recorded assessed by the treating physician as per routine care.
- xiii. Use and frequency change of phototherapy for psoriasis through the 24 months of treatment will be ascertained by a targeted question in the patient assessment.

# 6.0 Investigational Plan

This is a Canadian Post Marketing Observational Study utilizing a prospective cohort design. Patients are entered into the study cohort at the time of change of their Psoriasis treatment for any reason and are followed for a maximum of 24 months with recommended assessments at 3, 6, 12, 18 and 24 months after baseline. Treatment of the patients and follow up will be according to the physician's judgment, regional regulations and the product monograph. Off-label use will not be permitted and these patients will not be included in the study. Dose changes including escalation will be allowed as per the physician's judgment for patients that were treated as per indication when they were enrolled in the study.

There will be 660 patients enrolled from the practices of approximately 30 - 40 dermatologists across Canada. The study sample will be randomly selected and proportional to the Canadian population and distribution of dermatologists in Canada.

The following patient cohorts will be defined:

i. Initiated treatment with a new topical agent that was not used before or already on treatment with a topical agent and not responding requiring a change of treatment

type, frequency or dose.

- ii. Initiated treatment with a new systemic agent that was not used before alone or in combination with topical agents.
- iii. Initiated on treatment with adalimumab alone or in combination with topical agents.

In the case that the patient is switched from one cohort to another during the course of the study, follow up will continue as per the study protocol. For these cases, the treatment will be considered as a time dependent variable in the assessment of the study outcomes. In addition, depending on the number of patients switching cohorts, separate cohorts may be defined to include those patients that change treatment during the study.

Effectiveness outcome measures will include changes in clinical outcomes and quality of life. Health economic assessments will be conducted to determine the impact of treatment on Psoriasis related burden of illness. The impact of Psoriasis and different treatments on work productivity will be assessed. The study will also identify prognostic factors for progression to Psoriatic Arthritis and treatment gaps in the detection and screening for articular and extra-articular manifestations. Regional differences within Canada with respect to the patient profile and the management of patients with Psoriasis will be described.

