### 2.4 Study Design

JSS Recherche médicale Medical Research

COMPLETE - PS Statistical Analysis Plan Version 3.0 July 23rd, 2015

Page 13 of 231

This is a Canadian Post Marketing Observational Study (PMOS) utilizing a prospective cohort design. Patients are entered into the study cohort at the time of change of their PS treatment for any reason and are followed for a maximum of 24 months with recommended assessments at 3, 6, 12, 18 and 24 months after baseline. Treatment of the patients and follow up will be according to the physician's judgment, regional regulations and the product monograph. Off-label use will not be permitted and these patients will not be included in the study. Dose changes including escalation will be allowed as per the physician's judgment for

There will be 660 patients enrolled from the practices of approximately 30 - 40 dermatologists across Canada. The study sample will be randomly selected and proportional to the Canadian population and distribution of dermatologists in Canada.

patients that were treated as per indication when they were enrolled in the study.

The following patient cohorts will be defined:

- 1. Initiated treatment with a new topical agent that was not used before or already on treatment with a topical agent and not responding requiring a change of treatment type, frequency or dose.
- 2. Initiated treatment with a new systemic agent that was not used before alone or in combination with topical agents.
- 3. Initiated on treatment with adalimumab alone or in combination with topical agents.

In the case that the patient is switched from one cohort to another during the course of the study, follow up will continue as per the study protocol. For these cases, the treatment will be considered as a time dependent variable in the assessment of the study outcomes. In

JSS Recherche médicale Medical Research

**COMPLETE - PS Statistical Analysis Plan** Version 3.0

July 23rd, 2015

Page 14 of 231

addition, depending on the number of patients switching cohorts, separate cohorts may be

defined to include those patients that change treatment during the study.

Effectiveness outcome measures will include changes in clinical outcomes and quality of

life. Health economic assessments will be conducted to determine the impact of treatment on

PS related burden of illness. The impact of PS and the different treatment approaches on

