3.5 Analysis Populations

All safety analyses will be based on the Safety population that will comprise all patients who signed the inform consent and received at least one dose of study medication. The remaining analyses, including the baseline profile of the patients and treatment effectiveness, will be based on the Intent-to-Treat (ITT) population that will comprise all patients who signed informed consent, meet the inclusion / exclusion criteria, and received at least one dose of study medication.

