## 3.8 Subject Demographics and Baseline Characteristics

Descriptive statistics consisting of the mean, median, standard deviation and 95% confidence interval of the mean for continuous scale variables and frequency distributions for categorical variables will be produced for the baseline characteristics. These descriptive

COMPLETE - PS Statistical Analysis Plan Version 3.0 July 23rd, 2015 Page 28 of 231

statistics will be produced for the study cohort as a whole and for the three treatment cohorts as described in section 2.4, and by Canadian regions.

Between-group differences with respect to baseline characteristics will be assessed for statistical significance with One Way Analysis of Variance (ANOVA) for continuous variables if normally distributed or the Kruskal Wallis test if not normally distributed, and the Chi-Square statistic or the Fisher's exact test for categorical variables. Variables for which a trend for statistical significance (P<0.15) or clinically important difference (more than 2–fold) is observed will be considered as potential confounders and will be included as covariates in the multivariable analyses or propensity score development described in the following sections.

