## 3.10 Analysis of the Primary Objective

For the primary objective, between-group differences with respect to achieving a PGA of "0" or "1" at six months will be assessed with simple logistic regression analysis and multivariate logistic regression models adjusting for potential confounders or the propensity score. In addition, a Generalized Estimating Equation (GEE) model will be used to compare

COMPLETE - PS Statistical Analysis Plan Version 3.0 July 23rd, 2015 Page 30 of 231

the three patient groups in terms of achieving a PGA of "0" or "1" over 24 months of treatment. Kaplan Meier based time to event (survival) analysis will be used with the log-rank test to assess the statistical significance of the between group differences. Cox's proportional hazards model will also be used to adjust for potential confounders or the propensity score.

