## 3.11 Analysis of the Secondary Objectives

Between groups differences with respect to the changes in the BSA, PGA, DLQI, PASQ, BDI, SF-36 WLQ from baseline to 24 months of treatment will be assessed with One Way ANOVA or repeated measures, mixed effects general linear model adjusting for potential confounders or the propensity score. Planned contrasts will be used to assess between group differences at the other follow up time points. Pairwise between group comparisons will be adjusted for multiplicity with the Tukey's Least Significance Test.

In order to better assess the impact of the treatment received and changes in the regimen the treatment will be handled as a time-dependent covariate in these analyses. Descriptive statistics will be used to assess the between-group differences in healthcare resource utilization and healthcare costs associated with PS. With respect to achieving therapeutic response end points and incidence of articular and extra-articular manifestations between group differences will be assessed with multivariate logistic regression while Cox proportional hazard models will be used to assess between group differences with respect to the time of achieving therapeutic response and first occurrence of articular and extra-articular manifestations.

Descriptive statistics will be used to assess the regional differences with respect to baseline patient characteristics and disease parameters. Descriptive statistics will also be used to assess the practice patterns of Canadian dermatologists in the management of patients with

### COMPLETE - PS Statistical Analysis Plan Version 3.0 July 23rd, 2015 Page 31 of 231

moderate to severe Plaque PS. The study cohort will be divided into Canadian regions as Quebec, Ontario, Maritimes and Western Canada.

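### Does the time-dependent treatment rule for switchers leave the primary PGA comparison open to confounding by earlier response?

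*Protocol*

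**What the plan says.** Protocol 6.0 defines three cohorts by the treatment started at entry: topical, systemic and adalimumab. Patients who move between cohorts stay in follow-up, and for them "the treatment will be considered as a time dependent variable in the assessment of the study outcomes". Depending on how many switch, "separate cohorts may be defined to include those patients that change treatment during the study". SAP 2.4, part of the SAP's protocol summary, carries the same rule: treatment will "be considered as a time dependent variable in the assessment of the study outcomes".

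The analysis methods are in SAP section 3.

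- **SAP 3.5** states that effectiveness analyses are "based on the Intent-to-Treat (ITT) population that will comprise all patients who signed informed consent", subject to eligibility and at least one dose.
- **SAP 3.8** produces baseline summaries "for the three treatment cohorts as described in section 2.4" and draws potential confounders from baseline differences between those cohorts. SAP 3.2 describes propensity scores for the same purpose.
- **SAP 3.10** gives logistic regression for PGA of 0 or 1 at six months. In addition, "a Generalized Estimating Equation (GEE) model will be used to compare" "the three patient groups in terms of achieving a PGA of" 0 or 1 over 24 months. Kaplan-Meier and Cox analyses follow. Switchers are not mentioned.
- **SAP 3.11**, on the secondary objectives, describes the models for change from baseline and then says "the treatment will be handled as a time-dependent covariate in these analyses".

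Protocol 10.2 has the equivalent sentence after both its primary-outcome paragraph and its change-from-baseline paragraph. Protocol 6.5.1 leaves treatment changes to the physician. Neither document gives an expected switching rate or reasons for switching during follow-up.

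**The concern.** The general rule covers the study outcomes without excluding the primary one, and SAP 3.10 does not exempt its models. An analyst could therefore classify each patient by the treatment in use at month 6. All the stated adjustment concerns baseline. If patients doing badly at month 3 are the ones who switch, those left on a treatment are enriched for early responders, and the receiving group gains patients with a poorer outlook. Baseline covariates do not fully remove that.

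The primary objective is a comparison between treatments, so the stake would be the main result. Depending on the direction of switching, the adalimumab advantage could be understated or overstated. Two analysts following the same text could also report different estimates, because starting treatment and treatment received answer different questions.

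**Working it through.** **Step 1: which reading does the text support?**

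| Place | Role | What it settles |
|---|---|---|
| Protocol 6.0, SAP 2.4 | Design description | Time-dependent treatment for switchers, outcome not specified |
| SAP 3.8 | Methods | Treatment cohorts are those defined in 2.4, that is, by treatment started at entry |
| SAP 3.10 | Methods, primary | Compares three patient groups; no rule for regrouping |
| SAP 3.11 | Methods, secondary | Time-dependent treatment, stated explicitly |

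The month-6 logistic model has one outcome and one treatment term per patient, so nothing in it can vary with time. Using it by current treatment would need a rule for assigning patients at month 6, and neither document contains one. The groups in SAP 3.10 are most naturally the entry cohorts. A time-varying treatment term fits repeated-measures models and the Cox model.

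**Step 2: what if current treatment were used at month 6?** There is no figure in the plan to reproduce, so this is an illustration.

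Inputs from the documents: response 50%, 40% and 32% on adalimumab, systemic and topical (Protocol 10.3), and group sizes 330:165:165 (Protocol 10.3, SAP 2.7).

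Assumptions: logit P(response) = treatment intercept + patient effect, with patient effect N(0, SD²), SD 1.5 or 2.5, and intercepts set to give the rates above. Month-3 non-responders switch once with probability 0.2 or 0.4. Comparator patients move to adalimumab; adalimumab patients move to systemic.

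Worked case, comparators switching at 0.4, SD 1.5:

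- Systemic switchers: 0.4 × 0.60 = 24%, or 39.6 of 165. Topical: 0.4 × 0.68 = 27.2%, or 44.9 of 165.
- Month-3 responders among those still on systemic: 40 / (100 − 24) = 52.6%, against 40% at the start. This enrichment is the source of the bias.
- Integrating over the patient effect, current-treatment response is 47.85% on adalimumab (330 + 39.6 + 44.9 = 414.5 patients) and 43.64% on systemic. The difference is 4.2 points.
- By entry cohort, adalimumab stays at 50% and systemic rises to 42.35%. The difference is 7.65 points.

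Adalimumab minus systemic at month 6, in points, where the treatments differ by 10:

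| Switching | Current, SD 1.5 | Current, SD 2.5 | Entry cohort |
|---|---|---|---|
| Comparators 20% | 7.2 | 5.5 | 8.8 |
| Comparators 40% | 4.2 | 0.6 | 7.6–7.7 |
| Adalimumab 20% | 14.0 | 16.4 | 9.1 |
| Adalimumab 40% | 17.7 | 22.5 | 8.1–8.2 |
| Both 20% | 11.4 | 12.3 | 7.9 |
| Both 40% | 12.7 | 14.4 | 5.8 |

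Comparator switching unrelated to PGA gives 9.9 to 10.1 by current treatment, so the distortion comes from response-driven switching.

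**Step 3: scale against sampling error.** The 95% half-width for 50% vs 40% with 330 and 165 patients is 1.96 × √(0.25/330 + 0.24/165) = 1.96 × 0.0470 = 9.2 points. Of the 12 current-treatment results, two differ from 10 by more than this: 0.6 (by 9.4) and 22.5 (by 12.5). Both need SD 2.5 and 40% switching.

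The illustration includes no baseline covariates. If they explained half the patient variance (a further assumption), then at SD 1.5 the values 7.2 and 4.2 become 8.6 and 7.0, and 14.0 and 17.7 become 12.1 and 14.0.

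**Step 4: the GEE.** In a five-visit simulation of the same patterns, current treatment with an independence working correlation gives 2.5 to 20.0, an exchangeable correlation gives 9.8 to 10.3, and grouping by entry cohort gives 6.8 to 9.5. Harm there needs both current-treatment grouping and an independence structure, and the SAP text available specifies neither. The mock table for this model is listed but its body is not in that text.

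**Step 5: would fixing the entry cohort be a clear gain?** With two-way switching at SD 1.5, current treatment is nearer 10: off by 1.4 against 2.1 at 20%, and by 2.7 against 4.2 at 40%. At SD 2.5 the two nearly tie (2.3 against 2.1; 4.4 against 4.2). In the exchangeable GEE, current treatment is nearer throughout. Neither choice dominates.

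**The case for a change.** The strongest case for a change is that nothing explicit closes the question. The rule in Protocol 6.0 and SAP 2.4 is unrestricted. In Protocol 10.2 the time-dependent sentence follows the primary models as well as the secondary ones, so it can be read to reach both. The ITT definition says who is analysed, not in which group, and the titles of mock Tables 48 and 49 say only treatment group. The precedence rule in SAP 3.1.1 does not help, because SAP 3.10 sets no switching rule for it to favour. Separate switcher cohorts depend on the numbers seen, and SAP 3.12 plans an analysis after 335 completers, so the choice could be made with data in view. Response-driven switching is plausible, since inadequate response is among the listed reasons for changing treatment at entry. In a simulation with no true effect and switching towards adalimumab, the entry-cohort odds ratio against systemic stays at 0.99 to 1.01, while the current-treatment odds ratio falls as low as 0.67.

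The textual point stands: SAP 3.10 does not state how switchers are grouped. The mechanism also stands under its conditions. The step from there to a defect does not. Protocol 10.1 leaves the detail to the SAP, and the SAP places the time-dependent sentence under the secondary objectives. The figure of 0.67 needs SD 2.5 and 40% switching among month-3 non-responders. With no lasting prognosis beyond baseline, the bias disappears.

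**Conclusion.** No change to the plan follows. This is missing detail that analysts would fill sensibly, together with a fair trade-off over which effect to estimate. Read naturally, SAP 3.10 compares entry cohorts, and that comparison is not confounded by later switching. In the illustrated patterns it gives 5.8 to 9.1 points where the treatments differ by 10, which is dilution of a starting-treatment effect.

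The spread of 0.6 to 22.5 points arises only if month-6 patients are regrouped by current treatment, switching depends on earlier PGA, and substantial prognosis remains beyond the baseline covariates. For the GEE, an independence working correlation is needed as well. The switching rates, timing and patient variance are all assumed, so these figures show a mechanism and do not estimate bias in this study.

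Mandating the entry cohort would also set aside an aim that Protocol 10.2 states, to assess the treatment received, without a consistent gain in closeness to the 10-point difference. That choice belongs to the sponsor, and the plan is workable as it stands.
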